4.5 Kappa test

Kappa test will be used to analyze the equivalence of test reagent and comparison method (clinical reference standard). Using statistical software, Kappa test will be used to compare the results of test reagent and the comparison method (clinical reference standard), and k value will be calculated. When $k > 0.75$, the investigational reagent and comparison method show good consistency; when $k > 0.5$, the investigational reagent and clinical reference standard show general consistency.

$$Kappa = \frac{P_a - P_c}{1 - P_c}, \text{ where } P_a = \frac{A + D}{N}, P_c = \frac{\frac{(A+B)(A+C)}{N} + \frac{(B+D)(C+D)}{N}}{N}$$

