4.1 General Principles of Statistical Analysis

SAS 9.4 or above software will be used for statistical analysis. The sample size is calculated with PASS16. The statistical analysis of the validity and accuracy of test results is based on full analysis set (FAS) and per protocol set (PPS), and the safety analysis is based on safety set (SS). All statistical tests will be conducted on both sides and $P \leq 0.05$ will be considered statistically significant. (Unless otherwise specified)

The quantitative variables are expressed as mean, standard deviation, median, minimum, maximum, lower quartile (Q1) and upper quartile (Q3), while the categorical variables are expressed as the number and percentage of each category.

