4.3 Positive, Negative and Total Coincidence Rates Between Test Reagent and Comparison Method

For each genetic locus, fourfold tables will be used to calculate the positive and negative coincidence rates, positive and negative predictive values, total coincidence rate and their 95% confidence intervals. Using statistical software, Kappa test is used to determine statistical significance of the two methods.

Table 1 Result Summary of Clinical Trial Comparing Test Reagent and Comparison Method

Test Reagent	Comparison Method		Total
	Positive	Negative	
Positive	A	B	A+B
Negative	C	D	C+D
Total	A+C	B+D	A+B+C+D

Samples with mutant genotype detected are considered as positive, and samples without mutant genotype are considered as negative.

The calculation formula is:

$$\text{Positive coincidence rate} = A/(A+C) \times 100\%$$

$$\text{Negative compliance rate} = D/(B+D) \times 100\%$$

$$\text{Positive predictive value (PPV)} = A/(A+B) \times 100\%$$

$$\text{Negative predictive value (NPV)} = D/(C+D) \times 100\%$$

$$\text{Total coincidence rate} = (A+D)/(A+B+C+D) \times 100\%$$

The calculation formula of 95% confidence interval: $p \pm 1.96 \times [p(1-p)/n]^{1/2}$ (where P represents positive and negative coincidence rates, positive and negative predictive values and total coincidence rate, n presents the sample size. If $p > 0.9$, Wilson score method will be used for correction).

4.4 Sensitivity, Specificity and Total Coincidence Rate of Test Reagent and Clinical Reference Standard

Table 2 Result Summary of Test Reagent and Clinical Reference Standard

Test Reagent	Gold standard		Total
	Positive	Negative	
Positive	A (true-positive)	B (false-positive)	A+B
Negative	C (false-negative)	D (true-negative)	C+D
Total	A+C	B+D	A+B+C+D

Those with pathologically confirmed thyroid cancer will be considered as positive, while those without pathologically confirmed thyroid cancer whose FNA result is non-cancer without surgery will be considered as negative.

The test reagent and comparison method will be compared, but patients who fail to provide follow-up pathological results will not be included in the comparative

statistics of test reagent and clinical reference standard.

The calculation formula is:

$$\text{Sensitivity} = A/(A+C) \times 100\%$$

$$\text{Specificity} = D/(B+D) \times 100\%$$

$$\text{Total coincidence rate} = (A+D)/(A+B+C+D) \times 100\%$$

$$\text{Positive predictive value (PPV)} = A/(A+B) \times 100\%$$

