4.6 Clinical Evaluation Standard

1) Coincidence rate: Compared to the comparison method, if the lower limit of two-sided 95% confidence interval for both positive and negative coincidence rates of BRAF and TERT genes are greater than the 85% of preset target value, the statistical hypothesis is valid and in good agreement with the comparison method; otherwise, the statistical hypothesis is invalid, and the agreement with comparison method is not acceptable.

2) Sensitivity and specificity: Compared to the clinical reference method, if the lower

limit of two-sided 95% confidence interval for the sensitivity of BRAF or TERT gene pooled detection is greater than 50% of the preset target value and the lower limit of two-sided 95% confidence interval for the sensitivity of BRAF or TERT gene pooled detection is greater than 80% of the preset target value, the statistical hypothesis is valid and the diagnostic accuracy is acceptable; otherwise the statistical hypothesis is invalid, and the diagnostic accuracy is not acceptable.

5 Quality Control Method

Quality control should be applied at every stage of the clinical trial to ensure that all data are reliable and correct. The quality control method is as follows:

- (1) Qualifications of researchers involved in the study Researchers involved in the clinical trial must have professional expertise, qualifications and competences in the clinical trial, and pass the qualification examination, and staffing should be relatively fixed.
- (2) Training and preliminary tests: The sponsor is responsible for the training of researchers before the start of clinical trial, so as to help clinical researchers fully understand the clinical trial protocol, the detection of investigational products, the filling of original records and forms, etc.
- (3) Laboratory quality control: Clinical laboratories should be strictly in accordance with the *Measures for the Administration of Clinical Gene Amplification Testing Laboratories in Medical Institutions* (MOH Office MA [2010] No. 194 or the current effective version) and other relevant administrative regulations of molecular biology laboratories and clinical gene amplification laboratories.
- (4) Only when the quality control of investigational products meets relevant requirements can the test data be valid.

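### The kappa significance test cannot show equivalence, and the kappa cut-offs in section 4.5 can contradict the acceptance rule in section 4.6 in both directions

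*Protocol*

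**What the plan says.** Four parts of the Protocol bear on kappa.

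- Section 4.5 gives its purpose: "Kappa test will be used to analyze the equivalence of test reagent and comparison method (clinical reference standard").
- Section 4.3 says that the "Kappa test is used to determine statistical significance of the two methods".
- Section 4.1 sets the general level: "All statistical tests will be conducted on both sides and $P \leq 0.05$ will be considered statistically significant".
- Section 4.5 then grades the size of the estimate. Against Sanger: "When $k > 0.75$, the investigational reagent and comparison method show good consistency". Against pathology or clinical diagnosis: "when $k > 0.5$, the investigational reagent and clinical reference standard show general consistency". No null value is stated for the test, and no confidence interval is specified for kappa.

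Section 4.6 holds the acceptance rule and does not mention kappa. Against Sanger, the lower two-sided 95% limits of both "coincidence rates of BRAF and TERT genes are greater than the 85% of preset target value"; "otherwise, the statistical hypothesis is invalid, and the agreement with comparison method is not acceptable". The criteria against the clinical reference are also set on lower 95% limits.

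**The concern.** A significance test of kappa, in its usual form, asks whether agreement exceeds chance. Two assays aimed at the same mutation will nearly always pass it, including when one of them misses most mutations. Calling the result an analysis of equivalence attaches a strong claim to a weak test.

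The verbal labels raise a second problem. They are read off the point estimate of kappa, whereas section 4.6 judges the coincidence rates, and accuracy against the clinical reference, on lower 95% limits. Kappa also mixes positive and negative coincidence with prevalence, so a fixed cut-off does not correspond to the 85% rule.

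At stake is a report in which section 4.5 calls consistency good while section 4.6 calls agreement unacceptable, or in which a kit performing as planned passes section 4.6 but misses the kappa label.

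**Working it through.** **Inputs.** Section 3.2.1.1: BRAF 78 positives (target 85%, expected 95%); TERT 40 positives (target 85%, expected 98%); 363 negatives for each gene (target 85%, expected 90%). Section 3.2.1.2: sensitivity 50% target, 60% expected; specificity 80% target, 90% expected; 70% cancers; 360 patients, hence 252 cancers and 108 non-cancers.

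**The plan's own figures.** The stated sample-size formula, with two-sided alpha 0.05 and 80% power (power is not stated; 80% is assumed because it fits and 90% does not), gives 78.02, 362.8 and 39.6 for the agreement part, and 193.8 and 107.4 for the diagnostic part. The plan states 78, 363, 40, 194 and 108. The margins are therefore reproduced, apart from 78.02 not being rounded up to 79.

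**Formulas.** From section 4.5: kappa = (Pa − Pc)/(1 − Pc), with Pa = (A+D)/N and Pc = [(A+B)(A+C) + (B+D)(C+D)]/N². For the test of kappa = 0, the null standard error is SE0 = √{Pc + Pc² − Σ rᵢcᵢ(rᵢ+cᵢ)} / [(1−Pc)√N], where rᵢ and cᵢ are the row and column proportions. Cells are expected counts, so some are fractional.

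**1. Significance without agreement.**
- TERT, 30% positive and 90% negative coincidence: A = 12, B = 36.3, C = 28, D = 326.7. Pa = 0.840, Pc = 0.805, kappa = 0.183, SE0 = 0.0495, z = 3.70, P = 0.0002. Positive coincidence is 12/40 = 30% (95% CI 15.8% to 44.2% by the section 4.3 formula).
- Clinical reference, 25% sensitivity and 90% specificity: A = 63, B = 10.8, C = 189, D = 97.2. Kappa = 0.102, SE0 = 0.0316, z = 3.23, P = 0.001.

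Both are clearly significant. Both kappas are far below 0.75 and 0.5, and both kits fail section 4.6.

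**2. Label earned, section 4.6 failed** (no false positives).
- BRAF 51/78: Pa = 414/441 = 0.9388; Pc = (51×78 + 363×390)/441² = 0.7484; kappa = 0.757. Positive coincidence 65.4% (CI 54.8% to 75.9%).
- TERT 25/40: Pa = 388/403 = 0.9628; Pc = (25×40 + 363×378)/403² = 0.8510; kappa = 0.7502, only just over the cut-off. Positive coincidence 62.5% (CI 47.5% to 77.5%).

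Both would be labelled good, although even the upper limits lie below 85%.

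**3. Planned performance, label missed.**
- BRAF 95%/90%: A = 74.1, B = 36.3, C = 3.9, D = 326.7. Pa = 0.9088, Pc = 0.6613, kappa = 0.73.
- TERT 98%/90%: A = 39.2, B = 36.3, C = 0.8, D = 326.7. Pa = 0.9079, Pc = 0.7506, kappa = 0.63.
- Clinical reference 60%/90%: A = 151.2, B = 10.8, C = 100.8, D = 97.2. Pa = 0.69, Pc = 0.48, kappa = 0.21/0.52 = 0.40.

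Simulating binomial tables with these margins and rates, the estimate exceeds its cut-off in about 30%, 0.4% and 0.6% of trials respectively.

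**4. Dependence on prevalence.** The Protocol gives no mutation prevalence, so other margins were tried as assumptions.
- BRAF at 200/200 or 540/360: 95%/90% gives kappa of about 0.85, so the shortfall in step 3 disappears. The conflict in step 2 remains: 80% positive coincidence with no false positives gives kappa 0.80 and 0.76, with lower limits of 74.5% and 76.6%.
- TERT at 45/855: 70% positive coincidence with no false positives gives kappa 0.82 (lower limit 56.6%), while 95%/90% gives only 0.45. Both conflicts remain.
- Clinical reference at 60% or 80% cancers: planned performance gives 0.46 or 0.32, still below 0.5.

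**The case against.** The strongest reply is that nothing rides on the P value. Section 4.5 goes straight on to grade consistency by the size of kappa, no sentence says that a small P is read as agreement, and section 4.6 decides without kappa. A reader might infer from sections 4.1, 4.3 and 4.5 that a kit missing 70% of mutations would be declared in agreement. The documents do not support that. With 30% positive coincidence and no false positives at all, kappa stays at or below about 0.46 at any prevalence, so the 0.75 label is out of reach, and the 85% rule fails as well. This part of the objection stands and limits the point to a secondary statement in the report.

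It is also fair that the null of kappa = 0 is inferred, and that the form of a kappa test or its interval may be left to a statistical analysis plan. What does not fall away is the stated text: the Protocol itself assigns a significance test to equivalence and fixes two numerical cut-offs. The cut-offs do not rescue section 4.5, because they conflict with section 4.6 and, at the planned margins, with the Protocol's own expected values.

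A tempting repair is to grant the good label only when the lower 95% limit of kappa exceeds 0.75. That would make matters worse: at the planned margins and expected values the kappa estimates themselves lie below 0.75.

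**Conclusion.** The point holds as a fault in a secondary analysis that should be corrected before reporting. A significant kappa is not evidence of equivalence: at the planned TERT margins it is reached (P = 0.0002) with only 30% positive coincidence. The kappa labels can disagree with section 4.6 in either direction. They can be earned with positive coincidence of 62.5% to 65%, and at the expected values they are missed with kappa of about 0.73, 0.63 and 0.40.

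No acceptance decision changes, because section 4.6 does not use kappa. The conclusion rests on two assumptions: the test is against kappa = 0, and the table margins equal the planned minimum sizes. With a much higher share of BRAF-positive samples, the BRAF shortfall at planned performance goes away; the other conflicts remained in every alternative tried.

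**What to change.** In sections 4.3 and 4.5, delete the kappa significance test and the reference to equivalence. Report kappa with its 95% confidence interval as a descriptive measure, without the 0.75 and 0.5 verdict labels and without a substitute rule on its lower limit. Add one sentence stating that agreement with Sanger and diagnostic accuracy are concluded from section 4.6 alone.

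The cost is wording in two sections, and the loss of a supportive P value and label in the report. No new data are needed, and the sample size and acceptance criteria are unaffected.

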4.6 Clinical Evaluation Standard

1) Coincidence rate: Compared to the comparison method, if the lower limit of two-sided 95% confidence interval for both positive and negative coincidence rates of BRAF and TERT genes are greater than the 85% of preset target value, the statistical hypothesis is valid and in good agreement with the comparison method; otherwise, the statistical hypothesis is invalid, and the agreement with comparison method is not acceptable.

2) Sensitivity and specificity: Compared to the clinical reference method, if the lower

limit of two-sided 95% confidence interval for the sensitivity of BRAF or TERT gene pooled detection is greater than 50% of the preset target value and the lower limit of two-sided 95% confidence interval for the sensitivity of BRAF or TERT gene pooled detection is greater than 80% of the preset target value, the statistical hypothesis is valid and the diagnostic accuracy is acceptable; otherwise the statistical hypothesis is invalid, and the diagnostic accuracy is not acceptable.

5 Quality Control Method

Quality control should be applied at every stage of the clinical trial to ensure that all data are reliable and correct. The quality control method is as follows:

- (1) Qualifications of researchers involved in the study Researchers involved in the clinical trial must have professional expertise, qualifications and competences in the clinical trial, and pass the qualification examination, and staffing should be relatively fixed.
- (2) Training and preliminary tests: The sponsor is responsible for the training of researchers before the start of clinical trial, so as to help clinical researchers fully understand the clinical trial protocol, the detection of investigational products, the filling of original records and forms, etc.
- (3) Laboratory quality control: Clinical laboratories should be strictly in accordance with the *Measures for the Administration of Clinical Gene Amplification Testing Laboratories in Medical Institutions* (MOH Office MA [2010] No. 194 or the current effective version) and other relevant administrative regulations of molecular biology laboratories and clinical gene amplification laboratories.
- (4) Only when the quality control of investigational products meets relevant requirements can the test data be valid.
- (5) Clinical trial monitoring: The monitor shall make a complete monitoring plan before the start of the clinical trial, and monitor the clinical trial according to the monitoring plan to ensure that the clinical trial is carried out according to the clinical protocol, and ensure the intactness and accuracy of the original test data and records.

6 Provisions for Protocol Amendment

Any modification of the protocol during the trial shall be explained, and the time, reason, process and filing of the change shall be elaborated in detail, and its influence on the evaluation of the overall study results shall be demonstrated. If the investigators modify the protocol and case report form during the trial, it must be approved by the ethics committee before continuing the clinical trial.

7 Ethical issues and explanations involved in the clinical trial

The purpose of this clinical trial is to evaluate the performance of human TERT/BRAF Gene Mutation Pooled Detection Kit (PCR-fluorescence probe method) in clinical application. All the samples used in this clinical trial are prospective samples, which are specially collected for this clinical trial and shall be accompanied by a copy of signed informed consent form from the patient.

8 Data Processing and Record Storage

Investigators should record all the items on the clinical trial case report form truthfully, in detail and carefully according to the filling requirements, so as to ensure that the contents in the form are complete, true and reliable. All observations and findings obtained from the clinical trial should be verified to ensure the reliability of data and ensure that all conclusions in clinical trials come from original data. The clinical trial personnel should truly fill in relevant clinical information and the test results of clinical trials, and have them reviewed and signed by a specially-assigned person.

All original data records generated by this clinical trial shall be filed and preserved by the clinical sites, and the retention period shall be determined by the sites, but shall not be less than 5 years upon the completion of the clinical trial.

9 Responsibilities of Involved Parties

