3.2.1.2 Sample Size of Diagnostic Performance Verification

$$n = \frac{\left[Z_{1-\alpha/2} \sqrt{P_0(1-P_0)} + Z_{1-\beta} \sqrt{P_T(1-P_T)} \right]^2}{(P_T - P_0)^2}$$

Where, n represents the sample size; $Z_{1-\alpha/2}$ and $Z_{1-\beta}$ are fractions of standard normal distribution, P_0 is the target value of the evaluation indicator, and P_T is

the expected value of the evaluation indicator for in vitro diagnostic reagents.

Samples with BRAF or TERT mutation detected by the test reagent are considered as positive, and samples without mutation are considered as negative.

The results of pathological examination and clinical diagnosis will be used for comparison method. Those with pathologically confirmed thyroid cancer will be considered as positive, while those without pathologically confirmed thyroid cancer whose clinical diagnosis is non-cancer without surgery will be considered as negative.

According to relevant literature reports and preclinical study results, if the target value of sensitivity for the test reagent and comparison method is up to 50% with the expected value up to 60%, the minimum sample size of positive control group is estimated to be 194. According to previous experience, the proportion of positive diagnosis upon postoperative pathological examination is generally more than 70%. If estimated as 70%, the overall sample size of prospectively enrolled patients is 278. The target specificity value is 80% with the expected value of 90%, the minimum sample size of negative control group is estimated to be 108. If the proportion of negative results obtained from the postoperative pathological examination is estimated as 30%, the overall sample size of prospectively enrolled patients is 360. For the final overall sample size calculated based on sensitivity and specificity, the larger one (360 cases) shall prevail. Considering the estimated dropout rate of 10%, the final actual overall sample size is 400.

It is planned to carry out the trial in at least three clinical sites, with the enrollment of no less than 300 samples at each site. In case of objective reasons, when the sample size is insufficient, appropriate adjustments can be made among the sites to ensure the overall sample size. If the relevant laws and regulations change during the trial, the latest laws and regulations shall prevail, and the number of samples should be statistically significant.

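### The success rule for diagnostic accuracy applies both limits, 50% and 80%, to sensitivity and sets none for specificity

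*Protocol*

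**What the plan says.** Section 3.2.1.2 sets the two diagnostic targets. For sensitivity: "if the target value of sensitivity for the test reagent and comparison method is up to 50% with the expected value up to 60"%, from which "the minimum sample size of positive control group is estimated to be 194". For specificity: "The target specificity value is 80% with the expected value of 90"%, which gives 108 non-cancers.

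Section 4.6, item 2, turns these targets into a pass/fail rule with two conditions joined by *and*. The first puts the lower 95% limit for sensitivity against 50%. The second concerns the lower limit of the "two-sided 95% confidence interval for the sensitivity of BRAF or TERT gene pooled detection is greater than 80% of the preset target value". If either is missed, diagnostic accuracy is declared not acceptable. Specificity appears in the item's heading and in neither condition.

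Item 1, on agreement with Sanger sequencing, words its limit in the same way: the lower limits must be such that they "are greater than the 85% of preset target value".

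Elsewhere, section 4.4 estimates specificity with a 95% interval but attaches no limit to it, and section 4.5 gives kappa labels for consistency.

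**The concern.** The 80% figure belongs to specificity in the sample size section and to sensitivity in the decision rule. Two things follow if the rule is applied as printed.

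- Sensitivity must clear 80% although it is planned at 60%. The 50% condition becomes redundant, because any result that clears 80% also clears 50%.
- Specificity has no acceptance limit. The 108 non-cancers, which set the 360 and then 400 patients in section 3.2.1.2, support no decision.

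There is also a wording fault. A limit given as a percentage of the preset target value can be read as a fraction of that target, which gives quite different numbers. The verdict on the clinical claim should not depend on how a reader repairs the sentence once the results are known.

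**Working it through.** **Inputs.** Targets and expected values: sensitivity 50% and 60%, specificity 80% and 90% (section 3.2.1.2). Alpha: 0.05, since "All statistical tests will be conducted on both sides" (section 4.1). Power: not stated; the z-values only "are fractions of standard normal distribution". I take 80%. Of one- or two-sided 5% tests with 80% or 90% power, only two-sided with 80% gives both 194 and 108. Interval: Wald, or Wilson if the estimate exceeds 0.9 (section 4.4).

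**1. The protocol's sample sizes reproduce.** With n = [z(1−α/2)·√(P0(1−P0)) + z(1−β)·√(PT(1−PT))]² / (PT−P0)²:

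- Sensitivity: [1.960·√(0.5·0.5) + 0.8416·√(0.6·0.4)]² / 0.1² = 193.85, so 194.
- Specificity: [1.960·√(0.8·0.2) + 0.8416·√(0.9·0.1)]² / 0.1² = 107.43, so 108.
- Overall: 194/0.7 = 277.1, so 278; 108/0.3 = 360; 360/0.9 = 400.

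The design therefore tests sensitivity against 50% and specificity against 80%. With 360 evaluable patients, 0.7 × 360 = 252 are expected to have cancer and 108 not.

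**2. An on-plan result under the rule as written.** With 116/194 = 59.8% observed, the lower limit is 0.598 − 1.96·√(0.598·0.402/194) = 52.9%. With 151/252 it is 53.9%. Both pass 50% and fail 80%.

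**3. What is needed to pass.** The smallest counts with a lower limit above 80% are 165/194 (85.1%; 0.851 − 1.96·√(0.851·0.149/194) = 80.0%, just above the limit) and 213/252 (84.5%).

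**4. Probability of passing as written** (exact binomial, limits read as absolute):

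| True sensitivity | 194 cancers | 252 cancers |
|---|---|---|
| 60% (planned) | 2.7 × 10⁻¹⁴ | 2.3 × 10⁻¹⁷ |
| 70% | 8.7 × 10⁻⁷ | 7.0 × 10⁻⁸ |
| 80% | 0.044 | 0.040 |
| 85% | 0.54 | 0.62 |
| 90% | 0.989 | 0.998 |

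**5. The fraction reading.** Applied to the sensitivity target, the two limits become 0.50 × 50% = 25% and 0.80 × 50% = 40%. The planned kit then passes with probability 0.9998 at 194 cancers. Item 1 becomes 0.85 × 85% = 72.25%. Changing only the second condition to specificity would give 0.80 × 80% = 64%. The same sentence thus yields near-certain failure or near-certain success, and as printed neither reading involves specificity.

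**6. The corrected rule.** The sensitivity lower limit exceeds 50% with probability 0.81 (194 cancers, at least 111 positive) or 0.89 (252, at least 142). The specificity lower limit exceeds 80% with probability 0.88 (108 non-cancers, at least 94 negative). Multiplying for independent groups gives 0.81 × 0.88 = 0.71 for 194/108 and 0.89 × 0.88 = 0.79 for 252/108. With all 400 evaluable (280/120) it is 0.92 × 0.91 = 0.84.

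**The case against.** The strongest reply is that this is a one-word slip that any reader would notice. The item heading and section 3.2.1.2 make the intended rule plain, and the design, data and estimates are untouched. That is very probably right about intent. It does not excuse the rule, because settling on the intended reading after the results are in would be a post hoc change to the only acceptance criterion for diagnostic accuracy.

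Other points are fair and limit the claim:

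- Near-certain failure holds for the absolute reading and a true sensitivity near 60%. A kit near 90% would pass, and on the fraction reading the planned kit would pass. Section 3.2.1.2, and the 85% targets in section 3.2.1.1 set against item 1, support the absolute reading.
- A kit that called every sample positive would satisfy item 2, but the trial would not endorse it: its negative coincidence rate in item 1 would be 0%, and its kappa against the clinical reference would be 0. Item 1 is still no substitute for specificity, because a kit that agrees perfectly with Sanger sequencing could find mutations in nodules that are not cancer.
- Specificity is estimated with an interval and has a target in section 3.2.1.2; what it lacks is an acceptance limit.
- The 108 non-cancers set the diagnostic sample size of 360 and then 400, not the whole trial. Section 3.2.1.1 needs at least 441 for BRAF agreement, and section 3.2.1.2 plans at least 300 samples at each of three or more sites.

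**Conclusion.** The point holds. Section 4.6, item 2, contradicts section 3.2.1.2, and nothing else in the protocol repairs it. Taken as written with absolute limits, it rejects a kit that performs as planned with a probability that differs from 1 by less than 10⁻¹³, and it places no requirement on specificity. The figures rest on the protocol's own interval, a true sensitivity of 60%, and 194 or 252 evaluable cancers. A larger number of cancers makes failure more certain, since 60% lies well below 80%. The likely cause is clerical, but the text governs the pass/fail decision and must be corrected.

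**What to change.** Rewrite item 2 so that success requires the lower two-sided 95% limit for sensitivity to exceed the target of 50%, and the lower two-sided 95% limit for specificity to exceed the target of 80%. In item 1, state that the lower limits must exceed the target of 85%. In all three places drop the form that makes the limit a percentage of a target.

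The cost is a short amendment, explained and approved by the ethics committee as section 6 requires, and made before the blind is broken. It needs no additional patients, samples or data, and the sample sizes in section 3.2.1.2 already match the corrected rule.
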